7.5 SECONDARY ENDPOINTS

7.5.1 Key secondary endpoints

This section is not applicable as no key secondary endpoint has been specified in the protocol.

7.5.2 Other secondary endpoints

7.5.2.1 Phase Ib escalation

This section is not applicable as no secondary endpoint has been specified in the protocol.

7.5.2.2 Phase Ib expansion cohort

PFS based on investigator's assessment

PFS based on investigator's assessment will be assessed based on the Kaplan-Meier method in the phase Ib expansion cohort. Point estimates together with confidence intervals (based on Greenwood's method) will be provided for median time to event and quartiles.

Changes in CTC response

The following imputation will be performed before the analysis, separately for each sample:

- o If the amount of specimen volume is 7.5mL as planned, the measured cell count will be taken for the analysis
- o If the amount of specimen volume is ≥ 5 mL and < 7.5, and number of cells is reported and is ≥ 10 then the expected number of cells for the planned

- specimen volume will be imputed using linear transformation: expected cell count=7.5/(actual amount of blood in mL)*(measured cell count)
- o If the specimen volume amount of blood is ≥5mL and <7.5, and number of cells is missing or is <10, then no imputation will be done and the number of cells will be set to missing for the analysis

Frequencies of patients with CTC reduction will be displayed.

The maximum decline (percentage) in CTC counts compared to baseline will be analyzed descriptively.

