5.2.2.2 Phase Ib expansion cohort

Progression-free survival (PFS) based on investigator assessment

The rules are the same as the ones described in Section 5.1.3.

Please note that the date of randomisation will be replaced by the date of the first treatment administration of any study medication.

Changes in CTC response

This is defined as a decline in CTC value from ≥ 5 to ≤ 5 cells per 7.5mL blood (called "specimen volume" within this section and Section 7.5.2.2 (R14-0865), for at least one post-baseline time-point.

Patients with a CTC value <5 cells per 7.5 ml blood at baseline, or with missing baseline value, are not taken into consideration for this endpoint. Patients with no post baseline value are considered as missing for this endpoint.

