In case there is no value within this timeframe (day 84 to 92), but the patient discontinued all treatments earlier than day 84, then the End of Treatment (EOT) value should be used. A PSA value will be taken as EOT value if the assessment was performed between the date of discontinuation of the last study medication until 7 days (included) after this date (according to the protocol schedule for the EOT visit (EOTV)).

In case there is no value within this timeframe (day 84 to 92), and the patient did not discontinue all treatments earlier than day 84, no earlier value will be taken as replacement, the assessment will be missing.

PSA response

PSA response is defined as a decline in PSA value >50% (with confirmation at least 3 weeks later) (R13-1642). See Section 5.1.2. for more details.

Changes in CTC response

Changes in CTCs will be evaluated using the following criteria:

- CTC reduction is defined as a decline in CTC value from ≥5 to <5 cells per 7.5mL blood (called "specimen volume" within this section and Section 7.5.2.3) (R14-0865), for at least one post-baseline time-point. Patients with a CTC value <5 cells per 7.5 mL blood at baseline, or with missing baseline value, are not taken into consideration for this endpoint.
- Maximum decline in CTC counts (in number of cells) compared to baseline that occurs at any point after treatment start, defined as the difference (absolute and percentage) between the minimum post-baseline CTC value and the baseline CTC value. Patients with missing baseline value are considered missing for this criterion.
- CTC status at week 12 (≥5 or <5 cells per 7.5mL blood)

Baseline value is the value collected before a patient starts treatment with trial medication. Patients with no post-baseline value are considered as missing for the three criteria.

For the criterion "CTC status at week 12", the nearest assessment to C4V1 (day 85) will be used, with following window:

- A later value, until one week after (day 92), can be used
- An earlier value, after four weeks in trial (day 29), can be used.

In case the patient discontinued the trial before the planned assessment, the EOT assessment will be used for this criterion in case it is the nearest to the target day.

In case it is needed for descriptive tables, multiple entries for one single time point in a patient will be assessed as follows:

- If only one valid value (with acceptable specimen volume or imputable value) is available, this one will be used

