This patient set includes all patients in the treated set who provide at least one PK parameter that was not excluded according to the description in Section 6.6.3 below. Thus, a patient will be included in the PKS, even if he contributes only one PK parameter value for one period to the statistical assessment.

Biomarker Sets

A patient set will be defined for each biomarker, if the data is available. These sets include all patients in the treated set who have at least one evaluable baseline value for a biomarker.

- BB: Blood Biomarkers Baseline measurements of free, dissociable and total IGF-1, free, dissociable and total IGF-2, total IGFBP-3 in serum and IGF bioactivity in heparin plasma
- o MSb: Mutational status of archival FFPE tumor samples, at baseline
- o mRNAS: Messenger RNA (mRNA) expression of IGF pathway related genes, e.g. tumor IGF-1 and IGF-2, at baseline
- o DCS: Relevant biomarkers related to IGF-1 and IGF-2 Downstream Cascade (e.g. pAkt) in tumour tissue, at baseline
- o PES: Protein Expression Set of IGF-1/2 in FFPE tumour sample, at baseline
- o CTCb: CTC baseline measurement

Biomarker sets will be used for the corresponding biomarker analyses, and the CTCb set will be used as well for the analysis of the secondary and further endpoints related to CTC assessments. In case one of the biomarker sets is identical or contains <5% difference in number of patients with the randomized set (or treated set in the phase Ib expansion part), then the randomized set (or treated set in the phase Ib expansion part) will be used and biomarker sets will not be considered at all.

• ECG Set (ECGS)

This patient set includes all patients in the treated set who do not have artificial cardiac pacemakers and have at least one on-treatment value for at least one ECG variable.

• ECG-PK Set

This patient set includes all patients in the ECG set who are

- o in the comparator group ('enzalutamide') or
- o in the 'xentuzumab+enzalutamide' groups and have at least one time-matching pair of valid xentuzumab plasma concentration and QTcF change from baseline (see Section 7.8.4).

The decisions whether

- o a concentration is considered valid or
- o a time deviation between PK blood sampling and ECG recording is acceptable will be made no later than at the final BRPM before DBL.

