6.6.3 PK parameters / biomarkers

Missing data and outliers of PK data are handled according to BI standards (3).

Missing biomarker data may be imputed. The rules will be described in the Unblinded Report Planning Meeting (URPM) minutes and/or in the CTR.

Plasma concentration data and parameters of a subject will be included in the statistical PK analyses if they are not flagged for exclusion due to a protocol violation relevant to the evaluation of PK or due to PK non-evaluability (as revealed during data analysis, based on the criteria specified below). Exclusion of a subject's data will be documented in the CTR.

Relevant protocol violations may be

- Incorrect trial medication taken, i.e. the subject received at least one dose of trial medication the subject was not assigned to
- Incorrect dose of trial medication taken
- Use of restricted medications.

Plasma concentrations and/or parameters of a subject will be considered as non-evaluable, if for example

- the subject experienced emesis that occurred at or before two times median tmax of the respective treatment (Median t_{max} is to be determined excluding the subjects experiencing emesis),
- missing samples/concentration data at important phases of PK disposition curve.

Exclusion of PK parameters

The analysis data set (ADS) ADPP contains column variables APEXC and APEXCO indicating inclusion/exclusion (APEXC) of a PK parameter and an analysis flag comment (APEXCO). All analyses based on the PKS are based on PK parameters with APEXC equal to "Included", regardless of the analysis flag comment APEXCO.

Exclusion of plasma concentrations

The ADS ADPC (PK concentrations per time-point) contains a column variable ACEXCO containing an analysis flag comment. Exclusion of a plasma concentration depends on the analysis flag comment ACEXCO. For example, if ACEXCO is set to 'ALL CALC', the value will be excluded for all types of analyses based on concentrations. If ACEXCO is set to 'DESC STATS' the value will be excluded from descriptive evaluations per planned time point. If ACEXCO contains the addition 'TIME VIOLATION' or 'TIME DEVIATION' the value can be used for further analyses based on actual times. If ACEXCO is set to 'HALF LIFE' the value will be excluded from half-life calculation only; the value is included for all other analyses.

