7 PLANNED ANALYSES

The labelling and display format of statistical parameters will follow BI standards (8).

Unless otherwise specified, outputs will be displayed separately for each part of the trial.

Descriptive statistics for continuous variables will generally contain number of patients in that patient set with non-missing values (N), Mean, Standard Deviation (SD), Minimum (Min), 25th percentile (Q1), Median, Q3 (75th percentile), Maximum (Max). In general, means, SDs, medians, Q1 and Q3 will be presented to one more decimal place than the raw data. Minima and maxima will be presented to the same number of decimal places as the raw data.

For time-to-event analysis tables, the set of statistics is: number of patients [N (%)], Number of patients with event [N (%)], Number of patients censored [N (%)], <Time to event> [months] followed by Q1 (25th percentile), Median, Q3 (75th percentile). If not specified otherwise, the duration as well as time to event will be displayed in months.

Tabulations of frequencies for categorical data will include all possible categories and will display the number of observations in a category as well as the percentage (%) relative to the respective treatment group total. Percentages will be rounded to one decimal place. In general a category "missing" will be displayed, if there are missing data for the corresponding variable. Percentages will also generally be based on all patients in the respective patient set whether they have non-missing values or not.

The primary analysis will include all treated (phase I escalation and expansion parts) or randomised patients (phase II part), following the ITT approach (as specified in Section 6.3).

Sort order for general categorical variables: If categories correspond to the collected categories on the eCRF and the table shells do not explicitly specify the ordering, the "default ordering" defined by the eCRF is to be used in such cases. If categories are derived the ordering as specified in the table shell document should be used; in general ordinal data (e.g. categorised continuous data) are to be displayed in ascending order.

The denominator of the main categories is defined by the number of patients in the used patient set. The main categories define the denominators of the subcategories. Subcategories should be indented and "[N (%)]" to be displayed only for the main category.

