7.5.2.3 Phase II

PFS based on central review

PFS based on central review will be analysed using the same methods as for the primary endpoint for phase II (see Section 7.4.3), including subgroup analyses, if deemed appropriate.

OS

OS will be analysed using the same methods as for the primary endpoint for phase II (see Section 7.4.3), including subgroup analyses, if deemed appropriate.

Time to PSA progression

Time to PSA progression will be analysed using a Cox proportional hazards model in the same way as the primary endpoint for phase II (see Section 7.4.3).

Maximum decline in PSA

Descriptive statistics for maximum decline in PSA will be displayed. This endpoint will also be explored graphically by means of a waterfall plot (using the percentage decline). All PSA assessments will be displayed in a longitudinal plot.

Percentage change in PSA at week 12

Descriptive statistics for percentage change in PSA at week 12 will be provided. This endpoint will also be explored graphically by means of a waterfall plot. All percentage changes in PSA will be displayed in a longitudinal plot.

PSA response

Descriptive statistics for PSA response will be provided. Confirmed as well as unconfirmed responses will be displayed.

Changes in CTC response

Imputations as specified in Sections 5.2.2 and 7.5.2.2 will be performed before the analysis, separately for each sample.

Frequencies of patients with CTC reduction will be displayed.

The maximum decline (percentage) in CTC counts compared to baseline will be analyzed descriptively and also explored graphically by means of a waterfall plot. All CTC assessments will be displayed in an overtime plot per patient.

Difference in proportions for week 12 status will be displayed by means of a contingency table, along with 95% confidence interval and a Fisher's exact test.

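### CTC samples of 5 to <7.5 mL are kept only when at least 10 cells are counted, so a short sample can never be scored below 5

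*SAP*

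**What the plan says.** SAP 7.5.2.2 sorts CTC samples by specimen volume. At 7.5 mL the measured count is used. At 5 to <7.5 mL, a count of 10 or more is multiplied by 7.5/volume and kept. In the same volume range, if the "number of cells is missing or is <10, then no imputation will be done and the number of cells will be set to missing". SAP 7.5.2.3 states that these imputations "will be performed before the analysis, separately for each sample" in phase II as well.

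CTC reduction (SAP 5.2.2.2 and 5.2.2.3) is a move from at least 5 to fewer than 5 cells per 7.5 mL at one or more post-baseline time-points. Patients below 5 at baseline, "or with missing baseline value, are not taken into consideration for this endpoint". Phase II adds maximum decline and week-12 status. For week-12 status the value nearest day 85 is used, and "An earlier value, after four weeks in trial (day 29), can be used".

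On analysis sets, SAP 6.3 says "the CTCb set will be used as well for the analysis of the secondary and further endpoints related to CTC assessments". Membership requires "at least one evaluable baseline value for a biomarker", unless the set differs from the randomised or treated set by less than 5%. SAP 6.6.3 adds "Missing biomarker data may be imputed", with rules left to the unblinded planning-meeting minutes or the report. SAP 7 says percentages are generally "based on all patients in the respective patient set whether they have non-missing values or not".

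**The concern.** Within short samples, the outcome value itself decides whether a result is missing. Counts that cannot be a response are kept, and every count that could be one is discarded, along with counts of 5-9 whose classification is not in doubt. The available text gives no reason for the 10-cell cut-off and no sensitivity analysis.

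CTC reduction is a secondary endpoint in the expansion cohort (about 25 patients) and in phase II (40 per arm). Only patients with a baseline of at least 5 count towards it, so one or two reclassified patients would show.

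**Working it through.** The plan states no expected CTC rate, power or share of short samples, so there is no figure to reproduce.

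**1. What follows from the rule alone.** The smallest value a retained short sample can take is 10 x 7.5/volume:

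| Volume (mL) | 5 | 6 | 7 | 7.49 |
|---|---|---|---|---|
| Smallest retained value | 15.0 | 12.5 | 10.7 | 10.01 |
| Largest raw count that would scale to <5 | 3 | 3 | 4 | 4 |

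The retained value always exceeds 10, so no short sample can be scored below 5. A short baseline with 5-9 raw cells is at least 5 per 7.5 mL whatever the missing volume held, yet the patient is dropped. Against scaling every reported count, the number scored as CTC reduction can only fall: discarded low values remove responders, and retained short values cannot create one.

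**2. One sample, volume unrelated to count.** Let q be the share of short samples, p5 the true probability of <5, and P10 the probability of a raw count of at least 10. Among non-missing samples:

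P(<5) = (1-q) x p5 / [(1-q) + q x P10]

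The multiplier of p5 is below 1 whenever q and P10 are positive. With p5 = P10 = 0.40 (assumed) and q = 0.10, this is 0.36/0.94 = 0.383. With missing samples left in the denominator it is 0.90 x 0.40 = 0.36.

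**3. CTC reduction by simulation (inputs assumed).** Baseline rates were gamma (shape 0.5 or 1.0, mean 20 or 40). Post-baseline rate was baseline x exp(N(-1.0 or -1.8, 1)) x exp(N(0, 0.6)) per sample, with 1, 2 or 4 post-baseline samples, giving 24 settings. Short volumes were uniform on 5-7.5 mL, with binomial thinning of the 7.5 mL Poisson count, and volume was independent of count. Simulation error of a difference is about 0.001.

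| Short share | Loss in reduction rate | Qualifying patients dropped at baseline |
|---|---|---|
| 5% | 0.009-0.015 | 0.8-1.5% |
| 10% | 0.019-0.030 | 1.6-3.0% |
| 20% (stress case) | 0.040-0.062 | not tabulated |

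One setting at 10% short (shape 0.5, mean 40, shift -1.0, four samples): true 0.452, SAP rule 0.430, every count scaled 0.454. With a single post-baseline sample, and patients without a usable value kept in the denominator, the loss reaches 0.033 at 5% and 0.065 at 10%. With four post-baseline samples, about 1 of 80 patients (5% short) or 2 of 80 (10%) gets a different result than under scaling.

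A separate model (shape 0.6, mean 30, median post-baseline ratio 0.5, one post-baseline sample) shows that the selectivity does the harm. At 10% short the rate among evaluable patients is 0.250 at full volume, 0.250 if all short samples are set to missing, and 0.230 under the SAP rule.

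**4. If volume depends on count.** Single sample, shape 0.5, mean 10.5, true proportion <5 of 0.495, non-missing denominator:
- short samples unrelated to rate (about 10% short): 0.479
- short samples three times as frequent above the median rate (about 10% short): 0.494
- short samples concentrated at rates of 5-12 (11.8% short overall): 0.519

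**5. Week-12 status.** Protocol 6.2.2 schedules CTC at C2D1, C3D1 and C5D1 (days 29, 57 and 113). The day 29-92 window therefore lets C2D1 replace a deleted C3D1 value. At 10% short, non-missing denominator, two arms, true then SAP rule:
- stable: 0.618/0.446, then 0.615/0.443
- declining: 0.746/0.566, then 0.733/0.552
- rebound: 0.494/0.343, then 0.500/0.346

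The between-arm difference moves by at most 0.002. Without the fallback it can grow (0.180 to 0.186) or shrink (0.101 to 0.097).

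**The case against.** The mechanism is not in dispute; its importance is. CTC reduction is one of several non-key secondary endpoints, its planned output is a frequency table, efficacy inference is exploratory (protocol 7.2), and the CTC criterion with a Fisher test, week-12 status, barely moves. Protocol 5.1.2.3 draws at least 10 mL, so short samples may be rare: at 2% short, four of the settings lose only 0.003-0.005. With about 29 qualifying patients per arm (40 x 0.73 under one assumed model), the standard error of a 45% rate is sqrt(0.45 x 0.55/29) = 0.09, larger than the bias. All of this stands and limits the size.

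The direction is also conditional, as step 4 shows; only the fall in the number of responders relative to scaling is certain. Some protection exists: any one post-baseline value below 5 is enough, a valid repeat at the same time-point is used if there is one, and a 'missing' category would show part of the loss. None of these restores a discarded count. The analysis-set question matters only for week-12 status, because a missing baseline already voids the other two criteria.

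The best argument for withholding low counts is measurement error near the threshold. For 3 cells in 5 mL, the other 2.5 mL has an expected 1.5 cells, and P(at most 1) = 0.56. Raw counts of 3-4 are misclassified 24% of the time when scaled. That supports caution at 3-4. It does not support discarding 5-9 (no error) or 0-2 (0.9% misclassified overall; the least certain case, 2 cells in 5 mL, is correct with probability 0.92).

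**Conclusion.** The concern holds. As written, the rule makes missingness depend on the outcome: a short sample can be scored only as a non-response, and a short baseline of 5-9 cells removes a patient known to qualify. These two facts need no assumption.

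The size does. With volume unrelated to count and the assumed count distributions, the CTC reduction rate is understated by 0.009-0.015 at 5% short samples and 0.019-0.030 at 10%. If volume is related to count, a non-missing proportion may be unbiased or overstated. The between-arm effect has no fixed direction on a non-missing denominator. Maximum decline loses its deepest values only among short samples. The rule should be changed, but it does not threaten the trial's main conclusion.

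**What to change.** Replace the two short-sample bullets in SAP 7.5.2.2 with one rule: for every 5 to <7.5 mL sample with a reported count, use 7.5/volume x count to derive the <5 or >=5 status and the maximum decline. Only unreported counts are missing. At 10% short this leaves an error of +0.001 to +0.003 in CTC reduction.

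If scaled counts near the threshold are unwelcome, the minimum change is to keep raw counts of 5-9 as >=5 and 0-2 as <5, leaving only 3-4 missing. The remaining loss at 10% short is 0.002-0.010. Keeping only 5-9 would leave most of the bias (0.015-0.026).

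Also:
- report short samples with fewer than 10 cells by arm;
- state the denominators for CTC reduction and week-12 status;
- say whether an evaluable baseline in SAP 6.3 is judged before or after this step;
- show the present rule as a sensitivity analysis.

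The cost is one SAP rule, its code and one table, on data already collected. The downside of full scaling is uncertain classification at raw counts of 3-4, which make up 16% of short samples with fewer than 10 cells in the assumed models.

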7.5.2.3 Phase II

PFS based on central review

PFS based on central review will be analysed using the same methods as for the primary endpoint for phase II (see Section 7.4.3), including subgroup analyses, if deemed appropriate.

OS

OS will be analysed using the same methods as for the primary endpoint for phase II (see Section 7.4.3), including subgroup analyses, if deemed appropriate.

Time to PSA progression

Time to PSA progression will be analysed using a Cox proportional hazards model in the same way as the primary endpoint for phase II (see Section 7.4.3).

Maximum decline in PSA

Descriptive statistics for maximum decline in PSA will be displayed. This endpoint will also be explored graphically by means of a waterfall plot (using the percentage decline). All PSA assessments will be displayed in a longitudinal plot.

Percentage change in PSA at week 12

Descriptive statistics for percentage change in PSA at week 12 will be provided. This endpoint will also be explored graphically by means of a waterfall plot. All percentage changes in PSA will be displayed in a longitudinal plot.

PSA response

Descriptive statistics for PSA response will be provided. Confirmed as well as unconfirmed responses will be displayed.

Changes in CTC response

Imputations as specified in Sections 5.2.2 and 7.5.2.2 will be performed before the analysis, separately for each sample.

Frequencies of patients with CTC reduction will be displayed.

The maximum decline (percentage) in CTC counts compared to baseline will be analyzed descriptively and also explored graphically by means of a waterfall plot. All CTC assessments will be displayed in an overtime plot per patient.

Difference in proportions for week 12 status will be displayed by means of a contingency table, along with 95% confidence interval and a Fisher's exact test.

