7.9.4 Potential surrogate biomarkers

If and only if PFS or OS study results are statistically significant, the CTC status at week 12 alone and in combination with lab parameters will be evaluated as potential surrogate for either PFS or OS using Prentice Criteria (R16-0801). The alpha level will be increased to 20% in order to account for the study size. The following lab parameters and their pairwise combinations will be investigated, if data allows: albumin, alkaline phosphatase, hemoglobin, lactate dehydrogenase. The time points for lab measures will be selected as close as possible

to the CTC status measure and must be on treatment. Details of the analyses are as in R16-0801 and will be described further in Cumulative Statistical Analysis Plan (CSAP).

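### The between-arm comparison of week-12 CTC status leaves out baseline CTC status, a small but avoidable loss of precision

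*SAP*

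**What the plan says.** SAP 5.2.2.3 (Phase II) sets three criteria for change in CTCs: reduction from ≥5 to <5 cells, counted only in patients who start at ≥5; maximum decline from baseline; and "CTC status at week 12", split at 5 cells per 7.5 mL with no reference to the starting value. SAP 4.2 notes that the third was added after the protocol.

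SAP 7.5.2.3 treats them differently. Reduction is shown as frequencies, and maximum decline descriptively and in a waterfall plot. Only week-12 status gets a between-arm comparison: "Difference in proportions for week 12 status will be displayed by means of a contingency table, along with 95% confidence interval", together with Fisher's exact test.

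SAP 6.3 says of the biomarker sets: "These sets include all patients in the treated set who have at least one evaluable baseline value for a biomarker". It adds that "the CTCb set will be used as well for the analysis of the secondary and further endpoints related to CTC assessments". If a biomarker set differs from the randomised set by less than 5% of patients, the randomised set is used instead.

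SAP 7.9.1 lists baseline CTC among the potentially prognostic biomarkers, and Protocol 5.1.2.3 also plans to evaluate CTC counts as prognostic. Protocol 3.3 and 7.5 give 40 patients per arm, randomised 1:1 with no stratification factor named.

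**The concern.** The outcome is a dichotomised count, and the same count is taken before treatment. A patient who starts below 5 and stays there scores the same at week 12 as one who falls from a high count. The arm that happens to receive more low-count patients will therefore tend to look better at week 12 whatever the treatment does. With 40 per arm and no stratification, such imbalance is common.

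Protocol 7.2 rests conclusions on the size of the observed differences in PFS and other efficacy endpoints. Noise in that size that collected data could remove is therefore worth removing, even in an exploratory trial. Elsewhere the SAP does adjust for baseline: the repeated-measures model for QTcF in SAP 7.8.4 includes it.

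**Working it through.** **The plan's own figures.** The documents give no rate, power or sample-size figure for any CTC endpoint, so there is none to reproduce. The Phase II sizing concerns PFS and does reproduce: Φ[(ln 0.8 − ln 0.65)/√(4/60)] = 0.789 against the stated 0.79.

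**Inputs.** From the documents: n = 40 per arm, simple 1:1 allocation. Assumed, because the documents are silent: π, the proportion with baseline ≥5; and a and b, the risks of week-12 status ≥5 in patients starting at ≥5 and at <5.

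**1. Baseline imbalance.** Its SD is √(2π(1−π)/n). With π = 0.5 this is √(2 × 0.25/40) = 0.112, about 11 points. It carries (a − b) times as much into the week-12 difference: with a = 0.6 and b = 0.1, 0.5 × 0.112 = 0.056. By simulation at π = 0.5, imbalance of at least 10 points arises in about 43% of randomisations and of at least 20 points in about 9%.

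**2. One imbalanced trial with no treatment effect.** Take baseline ≥5 in 16/40 versus 24/40, with risks 0.6 and 0.1. The expected week-12 difference is (16 − 24)/40 × 0.5 = −0.10. Fisher's test rejects in 6.9% of such trials, against 0.9% when the arms are balanced at 20 each. Averaged over randomisations it rejects in 3.1%.

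**3. Variance that stratifying can remove.** With p = πa + (1−π)b, the share of variance lying between baseline strata is π(1−π)(a−b)²/[p(1−p)]. For (π, a, b) = (0.5, 0.70, 0.10), p = 0.40 and the share is 0.25 × 0.36/0.24 = 37.5%. For (0.5, 0.40, 0.30), p = 0.35 and it is 0.25 × 0.01/0.2275 = 1.1%.

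**4. Power, with the two sources of gain kept apart.** Each scenario used 20,000 simulated trials, 40 per arm and a within-stratum odds ratio of 0.3. The chi-square tests are uncorrected Mantel-Haenszel tests, without and with stratification.

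| π, a, b | Variance share | Fisher | Unstratified chi-square | Stratified (CMH) | Gain from stratifying |
|---|---|---|---|---|---|
| 0.6, 0.75, 0.15 | 34.6% | 0.393 | 0.484 | 0.598 | 11.4 points |
| 0.5, 0.70, 0.10 | 37.5% | 0.318 | 0.400 | 0.524 | 12.4 points |
| 0.6, 0.65, 0.25 | 15.4% | 0.522 | 0.614 | 0.664 | 5.0 points |
| 0.5, 0.50, 0.20 | 9.9% | 0.459 | 0.551 | 0.573 | 2.2 points |
| 0.5, 0.45, 0.25 | 4.4% | 0.491 | 0.585 | 0.592 | 0.7 points |

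The step from Fisher to the unstratified chi-square is 8–9 points in every row and has nothing to do with baseline. With no treatment effect the rejection rates were 0.027–0.032 (Fisher), 0.047–0.056 (unstratified) and 0.044–0.051 (stratified). The mean Mantel-Haenszel and raw differences agreed to within 0.001 in every scenario, so stratifying changes the precision and not the quantity estimated.

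**The case against.** The strongest reply is that nothing here is invalid. An unadjusted comparison of randomised arms is unbiased over repeated randomisation, and its confidence interval already allows for chance imbalance. That stands. A reader might infer from the imbalanced example that the planned test is biased or has inflated error; its average type I error of about 0.03 shows otherwise.

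It can also be said that the benefit rests on assumed prognostic strength. That stands too. With a gap of 20 points between a and b, stratifying adds under 1 point of power. A reader who compared Fisher directly with CMH might credit baseline with the whole 10–21 points seen across the table, but 8–9 of those are Fisher's conservatism. An exact stratified test could give some of them back.

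Baseline does enter the companion criteria, and week-12 status is a legitimate landmark measure. But neither companion criterion has a between-arm test in SAP 7.5.2.3, so they do not supply the adjusted comparison. SAP 7.9.3 compares CTC measures over time between treatments but describes no baseline-adjusted analysis of week-12 status. Parts of the SAP on further endpoints are absent from the public text, so an adjusted CTC analysis there cannot be ruled out.

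Two further inferences fail. The CTCb set requires a baseline value, not a particular baseline status, so it does not select patients by high or low count. And SAP 7.9.4, where "the CTC status at week 12 alone and in combination with lab parameters will be evaluated as potential surrogate", analyses the status variable itself, and only if PFS or OS is significant. The test in 7.5.2.3 does not feed it.

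**Conclusion.** The point holds as a modest efficiency improvement to one exploratory secondary criterion. The planned comparison is valid but leaves out a baseline value that its own analysis set requires and that the SAP regards as potentially prognostic. Under the assumed rates, stratifying removes about 1–38% of the variance of the risk difference and adds about 1–12 points of power over an unstratified chi-square. The lower end applies if baseline status is only weakly prognostic. Dropping Fisher's test for an asymptotic one would add a separate 8–10 points. All these sizes depend on assumed CTC rates and on about 40 evaluable patients per arm. No conclusion about the primary endpoint is affected.

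**What to change.** In SAP 7.5.2.3, make the main comparison of week-12 CTC status the Mantel-Haenszel common risk difference with its 95% confidence interval and the CMH test, stratified by baseline CTC (≥5 versus <5), with an exact stratified test if a stratum is sparse. Keep the raw contingency table and Fisher's test as supportive. Add that, if the randomised set replaces the CTCb set under the 5% rule, the stratified analysis is run in patients with a baseline value.

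The cost is a sentence or two of SAP text and a few lines of SAS. No new data are needed. No patient is lost when the CTCb set is used, and fewer than 5% when the randomised set replaces it.
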